13.3. Adverse events of Special Interest for M7824 (Immediately reportable to the Sponsor)

Adverse events of special interest are required to be reported by the investigator to the Fundación GECP (SLCG/GECP) immediately (no more than 24 hours after learning of the event; see Section 13.5 for reporting instructions), despite not being serious. Adverse events of special interest for this study include the following:

- [REDACTED]
- [REDACTED]
- [REDACTED]
- [REDACTED]

13.4. Overdose and secondary malignancies

An overdose is defined as the accidental or intentional administration of any dose of a product that is considered both excessive and medically important. All occurrences of overdose must be reported as a SAE, indicating "life-threatening" as the seriousness.

Secondary malignancies are not always serious by regulatory definition, these events must be handled as SAEs.

13.5. SAEs and SUSARs reporting

All SAEs that occur within **30** days of the last administered study medication must be collected. Any SAE must be reported by submitting the completed Initial SAE Form in the online eCRF within 24 hours of awareness, even if they do not meet any of the seriousness criteria.

In case of the eCRF is unavailability, the submission could be done by sending the SAE form preferably by email to [contact] or by fax to the Fundación GECP (SLCG/GECP) Pharmacovigilance Office: [contact]. An appropriate SAE form (see appendix 3) should be used to report SAEs to Fundación GECP (SLCG/GECP). The paper SAE form has to be sent within the timeline period for reporting of 24 hours of awareness. **Once the eCRF system is available again, the SAE has to be completed and submitted by the site into the eCRF.**

If only limited information is initially available, a follow-up report is required to complete the information as soon as possible. (Note: Follow-up SAE reports should include the same SAE term(s) initially reported.)

The SAE outcome must be reported within 14 days after initial reporting by submitting the Follow up SAE Form in the online eCRF. In case the SAE is reported as ongoing after 14 days, a follow-up report has to be submitted again with the final outcome.

If an ongoing SAE changes in its grade, relationship to study drug, seriousness, SAE term or if new information becomes available, a new follow-up SAE report should be sent within 24 hours to the Fundación GECP (SLCG/GECP) using the same procedure after described.

Any SUSAR occurred during the trial will be notified under Spanish clinical regulation to the principal investigators, to the Health Authority (AEMPS) via Eudravigilance within the timelines specified in the Royal Decree 1090/2015 on clinical trials regarding the recording, evaluation and reporting of adverse events. Also, the autonomous regions will be informed about all SUSARs according to the current Spanish clinical trial regulation.

For any doubt please contact Fundación GECP (SLCG/GECP) pharmacovigilance office by this email: [contact] or by the [contact].

Also, Fundación GECP (SLCG/GECP) will ensure that all SAEs, SUSARs, AESIs and pregnancy reports in the clinical database (eCRF) are reported to the authorization holder y during the conduct of the study including periodic reconciliation.

13.6. Pregnancy

If, following initiation of the investigational product, it is subsequently discovered that a study participant is pregnant or may have been pregnant at the time of investigational product exposure, within 5 months after the last dose of M7824, the investigational product will be permanently discontinued.

Any pregnancy that occurs in a female partner of a male study participant should also be reported to the Fundación GECP (SLCG/GECP). Male patients will be instructed through the Informed Consent Form to immediately inform the investigator if his partner becomes pregnant during the chemotherapy treatment period or within 6 months after the last dose of chemotherapy. To allow Fundación GECP (SLCG/GECP) or designee to collect any pregnancy surveillance information from the female partner, the female partner must sign an informed consent form for disclosure of this information.

In both cases, the investigator must immediately notify to the Fundación GECP (SLCG/GECP) Pharmacovigilance Office by sending the Pregnancy form (see appendix 4) preferably by email to [contact] or by fax to the Fundación GECP (SLCG/GECP) Pharmacovigilance Office: [contact].

Follow-up information regarding the course of the pregnancy, including perinatal and neonatal outcome and, where applicable, offspring information, study discontinuation must be reported following the before procedure described during at least 1 year after child-bearing.

Any serious adverse events associated with the pregnancy (e.g., an event in the fetus, an event in the mother during or after the pregnancy, or a congenital anomaly/birth defect in the child) or abortion should be reported as a SAE.

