Bintralusp alfa is being developed as an immuno-oncology agent for treatment in a number of tumor types, including non-small cell lung cancer (NSCLC), biliary tract cancer (BTC), cervical cancer, and triple-negative breast cancer (TNBC).

A total of 689 participants participated in two phase I clinical trials (EMR200647-001 and MS200647-0008, as of 24 August 2018). Maximum tolerated dose (MTD) was not reached in either of the two studies at doses tested up to 30 mg/kg every 2 weeks (q2w). Each study had 1 dose-limiting toxicity (DLT) in 1 participant at the 20 mg/kg dose level. With no DLTs at other dose levels up to 30 mg/kg, bintralusp alfa at 30 mg/kg is considered tolerable. The emerging safety profile of bintralusp alfa (from EMR200647-001, MS200647-0008, MS200647-0005, MS200647-0024, MS200647-0037, MS200647-0047, and MS200647-0055) across tumor types investigated is manageable and consistent with other therapies targeting either PD-L1 or TGF- β pathways.

Treatment-emergent AEs of special interest (AESI) for bintralusp alfa are infusion-related reactions (IRRs), immune-related adverse events (irAEs), skin lesions possibly due to TGF- β inhibition and treatment-related anemia. Since 23 July 2017, IRRs (including hypersensitivity), irAEs / autoimmune disorders, and skin lesions with hyperkeratosis, keratoacanthoma, cutaneous squamous cell carcinoma possibly due to TGF- β inhibition are considered to be important identified risks with bintralusp alfa. Anemia, alterations in wound healing or

repair of tissue damage and embryofetal toxicity remained important potential risks. In addition, mucosal bleeding events are a potential risk for bintrafusp alfa.

Durable clinical activity of bintrafusp alfa was observed in a number of tumor types in the 2 Phase I studies (EMR200647-001 and MS200647-0008), specifically:

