10. For patients with HBV/HCV infection, it needs to be a controlled HBV/HCV infection on a stable dose of antiviral therapy, HBV viral load below the limit of quantification. HCV viral load below the limit of quantification.
11. All patients are notified of the investigational nature of this study and signed a written informed consent in accordance with institutional and national guidelines, including the Declaration of Helsinki prior to any trial-related intervention.
12. For female patients of childbearing potential, agreement (by patient and/or partner) to use a highly effective form(s) of contraception that results in a low failure rate (< 1% per year) when used consistently and correctly throughout the study and for at least 2 months after last bintralusp alfa treatment administration.
13. For male patients with female partners of childbearing potential, agreement (by patient and/or partner) to use a highly effective form(s) of contraception that results in a low failure rate (< 1% per year) when used consistently and correctly.
14. Oral contraception should always be combined with an additional contraceptive method because of a potential interaction with the study drugs. The same rules are valid for male patients involved in this clinical study if they have a partner of childbirth potential. Male patients must always use a condom. For male patients the duration of contraception after the last dose of bintralusp alfa is 4 months.
15. Women who are not postmenopausal (≥ 12 months of non-therapy-induced amenorrhea) or surgically sterile must have a negative serum pregnancy test result within 8 days prior to initiation of study drug.

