4. Adverse events: Changes from baseline abnormalities (new or worsened clinically significant ones) should be recorded as adverse events on the Adverse Event eCRF until this visit. For laboratory parameters, only grade 2 events will be reported as an AE. All the other events not related to laboratory values will be reported from grade 1. SAEs and AESIs must be recorded and followed from the subject written informed consent signature to 30 days from last dose of treatment.
5. Concomitant medications: Changes from baseline should be recorded on the eCRF until this visit (30 days from last dose of treatment).
6. Tumor assessment: if the end of treatment reason is other than disease progression the CT SCAN schedule will be performed every 8 weeks:

- a. **Chest and abdomen CT SCAN** with oral/IV contrast (unless contraindicated) to determine measurable disease according to mRECIST v1.1.

It is not mandatory to perform the tumor assessment in first follow up visit if the end of treatment reason is other than progression disease and a tumor assessment has been performed in the previous 8 weeks.

After the safety follow up visit, all the patients will be followed by a telephone call every 3 months until the end of study participation or last patient last visit.

End of study participation of the patients included in the study will be the date of the last study assessment.

9. Investigational Medicinal Product

Bintrafusp alfa (M7824) is the Investigational Medicinal Products (IMP) used in this trial. Merck will provide the IMPs at no cost for this trial.

Complete details of the trial drug logistics, distribution, packaging, labelling, storage and handling as well as accountability are described in the **BIMES drug supply manual** that will be provided in the Pharmacy site file to all the participant sites.

Description of the Investigational Medicinal Products

Bintralusp alfa (M7824) is a bifunctional fusion protein composed of the extracellular domain of the transforming growth factor β (TGF- β) receptor II (a TGF- β "trap") fused to a human immunoglobulin G1 antibody blocking programmed death-ligand 1 (PD-L1).

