Concomitant therapy consists of any medication (e.g., prescription drugs, over-the-counter drugs, vaccines, herbal or homeopathic remedies, nutritional supplements) used by a patient in addition to protocol-mandated treatment from 7 days prior to initiation of study drug to the study completion/discontinuation visit. All such medications should be reported to the investigator and recorded on the Concomitant Medications form in the eCRF.

Prohibited Concomitant Therapy

The following medications are prohibited while on study, unless otherwise noted:

- Cytoreductive therapy
- Radiotherapy delivered for non-palliative indications
- Immunotherapy, immunosuppressive drugs (that is, chemotherapy or systemic corticosteroids except for short-term treatment of allergic reactions or for the treatment of irAEs), or other experimental pharmaceutical products. Short-term administration of systemic steroid (that is, for allergic reactions or the management of irAEs is allowed).
- Live vaccine administration within 30 days before M7824. Vaccination with live vaccines while on study is prohibited. Administration of inactivated vaccines is allowed (for example, inactivated influenza vaccines)

The concomitant use of herbal therapies is not recommended because their pharmacokinetics, safety profiles, and potential drug-drug interactions are generally unknown. However, their use for patients on study is allowed at the discretion of the investigator provided that there are no known interactions with any study treatment. As noted above, herbal therapies intended for the treatment of cancer are prohibited.

Permitted Concomitant Therapy

Premedication with antihistamines may be administered for any M7824 infusions before day 1 week 1 and week 3. The following therapies should continue while patients are on study:

- Oral contraceptives.
- Hormone-replacement therapy.
- Prophylactic or therapeutic anticoagulation therapy, such as low molecular weight heparin (preferred) or warfarin at a stable dose level.
- Inactive influenza vaccinations.
- COVID-19 vaccination with an approved vaccine is allowed for patients included in the study
- Megestrol administered as an appetite stimulant.

- Inhaled corticosteroids for chronic obstructive pulmonary disease.
- Mineralocorticoids (e.g., fludrocortisone).
- Low-dose corticosteroids for patients with orthostatic hypotension or adrenocortical insufficiency (e.g. oral hidroaltesona 20 mg per day).
- G-CSF is allowed as per local standard.

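### Section 13.6 ties the male patient's partner-pregnancy prompt to chemotherapy, which this trial does not give, instead of to bintrafusp alfa (M7824)

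*Combined protocol and SAP*

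**What the plan says.** Section 13.6 deals with two kinds of pregnancy. For a participant's own pregnancy, the window is "within 5 months after the last dose of M7824". For a male participant's partner, the section first sets a general duty: "Any pregnancy that occurs in a female partner of a male study participant should also be reported" to the sponsor. It then describes the prompt that the consent form will give the man. He is to tell the investigator immediately if his partner becomes pregnant "during the chemotherapy treatment period or within 6 months after the last dose of chemotherapy".

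The contraception rules in Section 6.1 refer to the trial drug. Criterion 12, for women, requires contraception "for at least 2 months after last bintralusp alfa treatment administration". Criterion 14 adds: "For male patients the duration of contraception after the last dose of bintralusp alfa is 4 months".

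Section 9 says that bintrafusp alfa "is the Investigational Medicinal Products (IMP) used in this trial". Section 12 lists what is prohibited on study, including "Immunotherapy, immunosuppressive drugs (that is, chemotherapy or systemic corticosteroids", with an exception for short-term steroid use.

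**The concern.** The prompt depends on a treatment that no patient receives under this protocol. Chemotherapy enters the trial as prior therapy (Section 6.1, criterion 4), so these men have a real and different chemotherapy history to which the word can attach. Read literally, the 6 months run from chemotherapy given before enrollment, or from chemotherapy given after the trial. They do not run from exposure to M7824.

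This matters because Section 3.3 says of the trial drug that "repair of tissue damage and embryofetal toxicity remained important potential risks". If the consent form repeats the wording of Section 13.6, a man may not see that the prompt concerns the drug he is receiving now.

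**Working it through.** No sample size, power or error rate is involved. The check sets the relevant statements side by side.

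**1. Is there a chemotherapy treatment period in this trial?** No. Section 5 describes a single arm treated with M7824, Section 9 names no other trial drug, and Section 12 prohibits chemotherapy on study.

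**2. What do the post-treatment windows run from?**

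| Window | Length | Runs from | Place |
|---|---|---|---|
| Female contraception | 2 months | last bintrafusp alfa dose | 6.1, criterion 12 |
| Male contraception | 4 months | last bintrafusp alfa dose | 6.1, criterion 14 |
| Participant pregnancy | 5 months | last M7824 dose | 13.6 |
| Partner-pregnancy prompt | 6 months | last chemotherapy dose | 13.6 |

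Three of four refer to the trial drug and one does not. The 5-month window, which names M7824, stands in the paragraph just before the one that names chemotherapy. Nothing in the text gives a reason for treating the partner prompt differently.

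**3. What does the literal reading do?** Section 5 allows up to 2 years (24 months) of M7824. A 6-month window from chemotherapy that ended before enrollment closes less than 6 months into the trial. For a man still on M7824 after that, the prompt would have lapsed during exposure. This illustrates the literal wording. It does not estimate how many men would be affected, because the documents do not give the interval from prior chemotherapy, the length of treatment or how sites would read the sentence.

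**4. Is 6 months a defensible length once the drug is corrected?** No statement ties 6 months to M7824. Compared with the protocol's own windows, it exceeds male contraception by 6 − 4 = 2 months and the participant-pregnancy window by 6 − 5 = 1 month. Keeping it is therefore a conservative choice, not a documented requirement of the drug.

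**The case against.** The strongest reply is that little depends on the slip. The sponsor-reporting duty is unconditional, Section 13.6 asks for immediate notification in both situations, and the pregnancy form in Appendix 4 has a box for a female partner. Section 8.1.5 provides a telephone call every 3 months after the safety visit. Criteria 13 and 14 already connect partner pregnancy with this drug by requiring male contraception. In a single-drug trial, most site staff would take the phrase to mean study treatment. Patients act on the consent form, which was not available and may be correct.

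Much of this stands, and it keeps the consequence small. It does not make the sentence right. The reporting duty and the form come into play only once the site knows of the pregnancy, and the prompt is how Section 13.6 has the man tell the investigator. Calls 3 months apart do not replace an immediate report, and the visible text does not say that they ask about partner pregnancy. The charitable reading helps staff more than patients, for whom chemotherapy was an earlier treatment. If the consent form is correct, the protocol still disagrees with it.

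Two further points are fair: the window length is for the sponsor to confirm, and this is a drafting error, not a deliberate design decision. Neither removes the need to correct the drug name.

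**Conclusion.** The concern holds. The partner-pregnancy prompt in Section 13.6 names the wrong treatment, in 1 of the 4 stated post-treatment windows. It is a small error in a safety instruction and should be corrected. The primary endpoint, the analysis and dosing are unaffected, and the general duty to report partner pregnancies is sound.

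The conclusion about the protocol text needs no assumption. Any practical effect assumes that the consent form carries the same wording and that someone reads it literally; neither could be checked. The coverage gap is zero if chemotherapy is read as study treatment and otherwise cannot be sized from the documents.

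**What to change.** In the partner-pregnancy sentence of Section 13.6, replace chemotherapy with bintrafusp alfa (M7824) in both places, so that the treatment period and the last dose are those of the trial drug. Keep the 6 months as a conservative window, which the sponsor should confirm. Check the consent form and make the same correction if the wording appears there.

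The cost is one sentence in the protocol and possibly one in the consent form, with no new visits, tests or procedures. The change goes through the amendment and ethics review described in Sections 18.1 and 19.3. If the consent form proves correct, it can travel with the next amendment. If the consent form repeats the error, a revised form would also need approval.

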13.7. Other safety considerations

Any significant worsening noted during interim or final physical examinations, electrocardiograms, X-rays, and any other potential safety assessments, whether or not these procedures are required by the protocol, should also be recorded as a non-serious or serious AE, as appropriate, and reported accordingly.

14. Biological material and translational research

[figure not shown]
Several samples will be collected during the study. All the samples will be stored at:

[REDACTED]
[REDACTED]
[REDACTED]

The following samples will be collected:

- [REDACTED]
- [REDACTED]
- [REDACTED]
- [REDACTED]
- [REDACTED]

Please, refer to the **BIMES Samples Manual** for more information.

15. Case report forms and documentation

eCRFs will only be available on-line at the Remote Data Entry (RDE) facility of Fundación GECP for patient enrollment.

Only the patient pre-screening form will be used in a paper form and will be send scanned by email or by fax ([contact]) to obtain the pre-screening number.

Also, another exception will be a paper SAE form and pregnancy form that will be used only in case of eCRF system unavailability.

16. Statistical considerations

Three populations will be considered for different analyses:

- Per protocol population (PP): Per protocol population will consider patients that will receive a minimum of 3 cycles of treatment or that have at least the first tumor response evaluation carried out. Patients without any radiological evaluation who may die during the first 9 weeks will also be considered PP population. Patients without the first tumor response evaluation carried out but with a progression disease (also clinical progression) at 8 weeks will also be considered into PP population.
- Intention to treat analysis (ITT): Intention to treat analysis will include all patients that fulfill inclusion and exclusion criteria and will be registered into the clinical trial.
- Safety population (SFP): Safety population will include all patients that will be exposed to study treatment (bintrafusp alfa), whatever will be the quantity received

This study is designed to show that experimental treatment will achieve a median PFS of 4.5 months (expected median for standard scheme is 3 months which is equivalent to consider an improvement of 0.66 in terms of hazard ratio), with a statistical power of 90% and a one-sided type I error of 10%. On these bases and considering Lachin design, 45 pts are needed (44 or more events for null hypothesis and 43 or less events for alternative hypothesis) over a period of 18 months with a minimum median follow-up of 12 months to perform an exponential test. Considering a 5 % of drop-out patients and a hazard of 0.04 for dropouts a total sample size of 47 patients will be needed. In case of having 43 or less events during follow-up alternative hypothesis will be concluded and experimental treatment will be declared as promising.

The expected accrual rate is 2 patients per month for the first 6 months, increasing to 4-5 patients per month thereafter. Primary analysis is expected to be available 18 months after the inclusion of the first patient.

In order to reach the proposed sample size, if a patient initially enrolled in the study does not fulfil the inclusion criteria, they will be replaced by a new one subject that fulfil them, this replacement will ensure that the sample size will be the one calculated initially.

Reference: Lachin, John M (2000). Biostatistical Methods: The assessment of Relative Risks. John Wiley & Sons, New York, NY.

17. Criteria for termination of the trial

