Treatment will be administered until unacceptable toxicity, loss of clinical benefit, disease progression or completion of 2 years of therapy. If the patient has benefit after 2 years, the trial chair and the sponsor must be consulted to evaluate how to continue with the treatment.

If pseudoprogression is suspected, patients can continue with the study therapy until loss of clinical benefit as judged by the principal investigator. Prior to continuing with the study therapy, the trial chair of the study must be informed.

Statistical considerations:

This study is designed to show that experimental treatment will achieve a median PFS of 4.5 months (expected median for standard scheme is 3 months which is equivalent to consider an improvement of 0.66 in terms of hazard ratio), with a statistical power of 90% and a one-sided type I error of 10%. On these bases and considering Lachin design, 45 pts are needed (44 or more events for null hypothesis and 43 or less events for alternative hypothesis) over a period of 18 months with a minimum median follow-up of 12 months to perform an exponential test. Considering a 5 % of drop-out patients and a hazard of 0.04 for dropouts a total sample size of 47 patients will be needed. In

case of having 43 or less events during follow-up alternative hypothesis will be concluded and experimental treatment will be declared as promising.

The expected accrual rate is 2 patients per month for the first 6 months, increasing to 4-5 patients per month thereafter. Primary analysis is expected to be available 18 months after the inclusion of the first patient. In order to reach the proposed sample size, if a patient initially enrolled in the study does not fulfil the inclusion criteria, they will be replaced by a new one subject that fulfil them, this replacement will ensure that the sample size will be the one calculated initially.

Total trial duration: 3.5 years (1.5 years of recruitment, approximately 2 years of treatment and 1 month for the safety follow up)

Translational research:

Blood samples, tumor biopsy and malignant pleural effusion will be collected prior to initiating M7824 and when possible at tumor progression for the correlative studies.

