4.3. Exploratory objectives

- To correlate efficacy endpoints (PFS and ORR) with PD-L1 expression. This will be measured by PD-L1 immunohistochemistry in the central laboratory.
- To correlate efficacy endpoints (PFS and ORR) with activation of TGF-β pathway in tumor biopsies obtained at baseline and at tumor progression. This will be measured by SMAD2/3 and phospho-SMAD2/3 immunohistochemistry in tumor biopsies obtained at baseline and at tumor progression.
- To correlate efficacy endpoints (PFS and ORR) with TGF-β levels along with additional cytokines measured in serum obtained prior to initiation of immunotherapy and cytokines at tumor progression.
- To correlate efficacy endpoints (PFS and ORR) with TGF-β levels along with additional cytokines in pleural effusion obtained prior to initiation of immunotherapy and at tumor progression. To determine the immune cell subpopulations harvested in the pleural effusion at baseline and at tumor progression using flux cytometry in a subset of patients included in the study.
- To determine the predictive value of the immune groups based on the expression of cytotoxic T cells and Th2 cells signature measured in the tumor sample at baseline by using gene expression panels from NanoString technologies.

5. Trial design, duration and termination

[figure not shown]
This is an open-label, non-randomized, phase II, single arm, multi-center clinical trial.

Patients enrolled in the study will receive treatment with M7824 that will be administered at day 1 and day 14 or (2 weeks \pm 3 days) of 28 days cycle. Cycles will be administered until unacceptable toxicity, loss of clinical benefit, disease progression or completion of 2 years of therapy. If the patient has benefit after 2 years, the trial chair and the sponsor must be consulted to evaluate how to continue with the treatment.

Patient accrual is expected to be completed within 1.5 years excluding a run-in-period of 4-6 months. Treatment and follow-up are expected to extend the study duration to a total of 3.5 years. Patients will carry out a safety follow-up 1 month after the end of treatment independently of the cause of end of treatment. The study will end once safety follow-up has concluded.

The trial will end with the preparation of the final report, scheduled for 4.5 years after the inclusion of the first patient approximately.

Study schema:

6. Patient selection

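### Declaring the drug promising on 43 or fewer events ignores person-time and does not give 10% type I error and 90% power together in any setting examined

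*Combined protocol and SAP*

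**What the plan says.** Section 16, repeated in the statistical part of the Section 1 summary, assumes a median PFS of 3 months under the null and 4.5 months under the alternative, with power 90% and one-sided type I error 10%. Its design statement is "45 pts are needed (44 or more events for null hypothesis and 43 or less events for alternative hypothesis". The time frame attached to this statement, and the only mention of a test, is "over a period of 18 months with a minimum median follow-up of 12 months to perform an exponential test". Dropout enters as "Considering a 5 % of drop-out patients and a hazard of 0.04 for dropouts a total sample size of 47 patients will be needed". The success criterion is "In case of having 43 or less events during follow-up alternative hypothesis will be concluded and experimental treatment will be declared as promising".

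On timing, the same section gives the recruitment forecast "The expected accrual rate is 2 patients per month for the first 6 months, increasing to 4-5 patients per month thereafter". For the date of the main result it states "Primary analysis is expected to be available 18 months after the inclusion of the first patient". Section 5 adds "Patient accrual is expected to be completed within 1.5 years", excluding a run-in period.

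The rule comes with no person-time, test statistic, critical median or fixed cut-off date. Nor does the plan say whether 43 applies to 45 or to 47 patients. No other efficacy success criterion appears in the documents.

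**The concern.** An exponential test compares the number of events with the time at risk. A bare count does not. Cut the data early, or lose patients, and the count falls whatever the drug does, so an inactive drug passes. Follow everyone for long enough and nearly all progress, so a drug with the target median fails. The error rates therefore depend on cut-off and dropout, which the plan leaves open: a minimum median follow-up of 12 months and an analysis at month 18 do not fit together at the stated accrual. This count is the trial's only go/no-go criterion, and it can be wrong in either direction.

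**Working it through.** **Inputs (Section 16).** λ0 = ln 2/3 = 0.2310 and λ1 = ln 2/4.5 = 0.1540 per month; N = 45 or 47; accrual either uniform over 18 months or 2 per month for 6 months and then 4, 4.5 or 5 per month; dropout hazard g = 0, 0.04/12 or 0.04 per month, because the unit is not given. PFS is taken as exponential and dropout as independent.

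**The plan's N.** On the hazard scale, N = [1.2816·λ0/√p0 + 1.2816·λ1/√p1]² / (λ0 − λ1)². Uniform accrual over 18 months with a cut at month 30 gives p0 = 0.9852 and p1 = 0.9467, so N = 42.35, i.e. 43. With 12 months of follow-up for every patient (p0 = 0.9375, p1 = 0.8425), the log-hazard version gives (1.2816/√0.9375 + 1.2816/√0.8425)² / (ln 1.5)² = 45.0. Then 45 × 1.05 = 47.25. So 45 and 47 are reasonable for a person-time test.

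**Where 44 and 43 may come from.** Expected events for N = 45 at 18 + 12 months are 45 × 0.9852 = 44.3 under the null and 45 × 0.9467 = 42.6 under the alternative, which round to 44 and 43. That would make them expected counts, not a critical value. This origin is inferred; the plan does not state it.

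**Timing.** Put the first patient at month 0 and enter the rest at the stated rates. The last patient enters at month 12.4-14.5. The median patient enters at month 8.0 (N = 45, 5 per month) to 8.75 (N = 47, 4 per month), so median follow-up at month 18 is about 9.3-10.0 months. It reaches 12 months only at about month 20.0-20.75.

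**Error rates of the rule.** P(event by follow-up time f) = λ/(λ+g) × (1 − exp(−(λ+g)f)). The pass probability is P(D ≤ 43), binomial for uniform accrual or common follow-up and Poisson-binomial for the stated accrual. Example, N = 45, 18 + 12 months, g = 0: 1 − 0.9852^45 − 45 × 0.9852^44 × 0.0148 = 1 − 0.511 − 0.346 = 14.3% under the null; with 0.9467 it is 1 − 0.085 − 0.216 = 69.9% under the alternative.

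| Setting | N = 45: type I / power | N = 47: type I / power |
|---|---|---|
| 18 + 12 months, no dropout | 14.3% / 69.9% | 0.5% / 24.0% |
| Same, 0.04 per year | 36% / 83% | 4% / 42% |
| Same, 0.04 per month | 99.5% / over 99% | 94.5% / over 99% |
| Every patient followed 12 months, no dropout | 78% / 99.6% | 34% / 95% |
| Stated accrual, median follow-up 12 months, no dropout | 85-89% / over 99% | 46-55% / 97-98% |
| Stated accrual, month 18, no dropout | 97-99% / about 100% | 85-96% / about 100% |

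At month 18 the null itself predicts only about 38-41 events, so 43 or fewer is the normal result for an inactive drug.

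**Sweep.** N = 45 and 47; the dropout readings above plus 5% over 12, 18 or 30 months; common follow-up, uniform accrual over 12, 15 or 18 months, and the stated accrual; cut-offs out to month 60. No setting met both rates. With type I error at most 10%, the best power was 79%; with power at least 90%, the lowest type I error was 21%. Using the stated hazard ratio of 0.66 in place of 3/4.5 = 0.667 moves these to 80.3% and 19.8%.

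**Dropout.** Over 18 + 12 months, 0.04 per month implies 14.6% (null) to 20.1% (alternative) of patients dropping out before an event; 0.04 per year implies 1.4% to 2.0%.

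**Comparison.** The exponential test, simulated at the cut-off with 12 months' median follow-up under the stated accrual, gave type I error 10.3% and power of 90-91% with no dropout, about the same with 0.04 per year, and 87-88% with 0.04 per month.

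**The case against.** The plan does name an exponential test, so the 43/44 figures might be only illustrative. The text does not read that way: it says the alternative is concluded on the count. If illustration was meant, relabelling the figures settles it. A count of 43 could serve as a critical value at a total person-time fixed at about 229 person-months (type I error 9.3%, power 91.2%). The plan fixes no person-time, and that would need 229.4 × 0.2310 = 53 expected null events from at most 47 patients.

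Several qualifications stand:

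- 45 is the number before the dropout allowance, so the rows combining 45 with dropout carry less weight than those for 47.
- A hazard of 0.04 per year is roughly compatible with 5%: 1 − exp(−0.04 × 1.25) = 4.9% at 15 months. A monthly hazard would need 50-51 patients by the sample-size formula, so it fits 47 poorly. The missing unit is a minor point.
- Month 18 is a forecast, whereas the 12-month median is worded as a minimum. The month-18 row breaks that minimum.
- All these figures treat progression as observed continuously, but Section 8.1.3 scans every 8 weeks. If true median PFS is 3 months and every event is dated at the next scan (a worst case, since deaths are not), simulated type I error of the exponential test is about 60%. It is lower if the 3-month benchmark is itself scan-based. This affects any PFS test against that benchmark.

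None of these rescues the count rule.

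**Conclusion.** The concern holds, and the rule must be changed before it is used. The sample size supports 10% and 90% with a person-time test; the decision rule does not deliver them. For 47 patients without dropout, it runs from 0.5% type I error with 24% power (18 + 12 months) to 85-96% type I error (month 18). The plan's text does not settle which applies. The results assume exponential PFS and independent dropout; the first is the plan's own design assumption. The unstated dropout unit is covered by the range shown.

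**What to change.** In Sections 1 and 16, drop the 43/44-event rule as the decision criterion, or relabel the figures as expected counts. Decide with the exponential test: with d PFS events and X total PFS person-months, declare the treatment promising if 2 × 0.231 × X exceeds the 90th percentile of chi-square on 2d degrees of freedom. This means the one-sided 90% lower limit for median PFS lies above 3 months. The critical observed median is about 3.6 months. Censored patients contribute their time at risk.

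Then fix one cut-off and state the power there. Stated accrual means the monthly rates; the uniform column uses 18 months of accrual; neither includes dropout.

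| Option | Stated accrual | Uniform 18 months |
|---|---|---|
| A: median follow-up 12 months | month 20-21, 37-39 events under the alternative, power 90-91% | month 21, 35-37 events, power 89-90% |
| B: month 18 | 34-36 events, power 88-90% | 30-31 events, power 85-86% |
| C: 41 events (exact power 90.3%; 40 give 89.8%) | about month 22-25 | about month 24-27 |

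Option B means giving up the 12-month median condition; with 0.04 per month its power falls to 85-87% (stated accrual) or 82-83% (uniform). Option C needs a calendar fallback: at 0.04 per month, expected events under the alternative never exceed 47 × 0.1540/0.1940 = 37.3.

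State the unit of the 0.04 hazard and reconcile it with 5%. Say whether the 3-month benchmark rests on a comparable scan schedule.

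The cost is protocol wording only, with no added patients or data. At the stated accrual the analysis comes 2-3 months after month 18 under A and 4-7 months after under C; under B it stays at month 18 with slightly lower power. With censoring the chi-square test is approximate (simulated type I error 10-11%).
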